4.1.3. Safety Objective

To demonstrate safety in using the Relivion™ device.

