11.7. Statistical Analysis

11.7.1. General Considerations

Statistical analyses will be performed using SAS® v9.4 (SAS Institute, Cary NC, USA). Statistical analyses and reporting will be performed in compliance with FDA Guidance E6 GCP, 21 CFR part 812, E9 and ISO 14155.

All statistical tests will be two-sided. The required significance level of findings will be equal to or lower than 5%, nominal p-values will be presented. Where confidence limits are appropriate, the confidence level will be 95%.

Continuous variables will be summarized by a mean, standard deviation, minimum, median and maximum and categorical variables by a count and percentage. For comparison of means (continuous variables), the two-sample t-test or the Wilcoxon rank sum test will be used as appropriate. For comparison of proportions (categorical variables), the chi-squared test or Fisher's exact test will be used as appropriate.

If multiple measurements are taken in a single patient, statistics described below will be appropriately modified to accommodate the within patient correlation.

Deviations from the planned analysis will be described, with proper justification, in the clinical study report.

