11.7.2. Significance Level and Handling of Type I Error

Type I Error

The overall significance level for this study is 5% using two-tailed tests, except for treatment by site interaction that will be tested at a significance level of 10%.

Hierarchy Approach for Secondary Endpoint Analysis

The hierarchy approach will be adopted for the primary and secondary endpoints to control type I error due to multiple endpoint testing. Thus, the primary endpoint will first be tested and only if $p < 0.05$, will the secondary endpoints be tested. For the three secondary performance endpoints, the Benjamini–Hochberg step-up method will be used to adjust the p-values.

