11.7.5. Efficacy Analysis

Primary Efficacy Analyses

The primary endpoint is the proportion (%) of patients reporting reduction in their pain level 2 hours post-treatment without rescue medications from severe or moderate to mild or no pain, or from mild to no pain, in their first treated eligible (per **Section 9.1.6**) migraine attack (excluding the "self-practice" treatment). A count and percentage of subjects reporting such headache pain reduction without rescue medications will be calculated and presented for both study groups, each with a two-sided 95% exact confidence interval. The groups will be compared with a chi-squared test and a Fisher's exact test.

If the null hypothesis is rejected in favor of the alternative hypothesis and the proportion (%) of subjects responding to this endpoint in the active group is greater than that of the sham group, the study will be deemed successful.

The primary endpoint will also be evaluated stratified by center using a Mantel-Haenszel test to assess the center by group interaction.

A sensitivity analysis of the primary end-point will be performed to assess the impact of missing data on the study outcome. This will be performed using several possible imputation methods.

Subset Analyses of Primary Endpoint

Adjustment for other covariates such as demographics or other baseline patient characteristics may be performed by adding these variables into a logistic regression model.

Subgroup analysis will be performed and reported by adding the variables listed below to a logistic regression model:

- use of migraine medications
- blinding assessment
- US vs. OUS sites

Secondary Efficacy Analyses

The secondary efficacy variables will be summarized by a count and percentage and compared with a chi-squared test and a Fisher's exact test.

Exploratory Analyses

The exploratory variables will be summarized by a count and percentage and compared with a chi-squared test and a Fisher's exact test.

Global Impression of Effect will also be summarized by descriptive statistics per treatment group and compared between the groups with a t-test.

Frequency of use of rescue medications will be summarized by descriptive statistics per treatment group and compared between the groups with a t-test.

Safety Analysis

The primary safety variable, the cumulative incidence (and 95% CI) of device related adverse events (AEs) throughout the study, will be presented in tabular format and will include incidence tables by severity.

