Adverse event rates will be compared between the study groups with a Fisher's exact test.

Serious adverse events will be listed and discussed individually.

Treatment tolerability will be compared between the study groups. The number and percent of subjects who fail to complete the study and the number and percent of subjects who fail to complete the study because of Adverse Events will be presented as well.

Handling of Missing Data

Multiple imputation for binary data will be used as the primary imputation method in the case of missing data for the primary efficacy end-point.

Additional sensitivity analysis of the primary end-point will be performed to assess the impact of missing data on the study outcome using possible imputation methods for binary data:

 Neurolief Brain Innovation	THE RIME STUDY: ABRIDGED CLINICAL INVESTIGATION PLAN	Doc No.: CL-CIP-001 Abridged Ref Rev: REV.2 / 11JUN2019 Pg. 39 of 41
--	---	---

Observed Data: Use only subjects with non-missing pain data and who did not withdraw early from study

Dropout/AE Imputation: A subject with no post baseline measurement of pain or a subject withdrawn due to an adverse event or treatment intolerance should be considered as a nonresponder for this analysis.

Best Case Scenario: Assume all visits with missing pain data in active group are successes. Assume all subjects in the sham group with missing pain data are failures.

Worst Case Scenario: Assume all visits with missing pain data in active group are failures. Assume all subjects in the sham group with missing data are successes.

Imputation of missing data may be performed on secondary and exploratory endpoints as well.

Pooling

Subgroup analysis of the primary efficacy endpoint by center, and US vs OUS, will be used to evaluate the poolability of the results. The significance of center-to-center variability in treatment effect will be evaluated by including an interaction term of treatment group by center in a logistic regression model. In the case that poolability is questionable, the reasons for differential treatment effect, such as subject and clinical characteristics, will be investigated and reported.

12. References

2. See, World Health Organization, Headache Disorders, available at <http://www.who.int/mediaacentre/factsheets/fs277/en/>.

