4.4 Per-protocol (PP) analysis set

The per-protocol (PP) analysis set will include all subjects in the mITT population who completed at least one eligible attack in compliance with the protocol and have no major protocol deviations. Subjects in the PP population will be analyzed as-treated.

Major protocol deviations defined as deviations which may impact subject safety, alter the risk/benefit ratio, compromise the integrity of the study primary end point data include, but are not limited to:

- Study treatment deviation for first eligible attack, e.g. baseline diary reported after treatment initiation, diary reported after treatment start, Baseline diary reported more than 30 minutes prior to the initiation of

treatment.

- PRO report outside of window for first eligible attack.

4.5

Statistical Analysis of Analysis Sets

As discussed in the introduction section to the SAP, a technical issue may have rendered the study device ineffective for those subjects treated prior to May 31, 2019. Since the treatments may not have been therapeutic, including them in the primary safety analysis may lead to under reporting of safety events. Consequently, the ITT data analysis set will serve as the principal data analysis set for the safety analyses. The safety analyses will also be performed on the Full Analysis set.

The mITT data analysis set will serve as the principal data analysis set for the efficacy analyses.

The primary and secondary efficacy assessments will also be performed on the per protocol (PP) and the ITT analysis sets.

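### No estimate or interval is planned for the excess adverse-event rate over sham, and a non-significant Fisher test could not exclude a sizeable excess of uncommon events

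*Protocol*

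**What the plan says.** Protocol 4.1.3 states the safety objective: "To demonstrate safety in using the Relivion™ device". No safety hypothesis, margin, performance goal or power goes with it.

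The safety part of protocol 11.7.5 plans three things that matter here:

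- Incidence: "The primary safety variable, the cumulative incidence (and 95% CI) of device related adverse events (AEs) throughout the study, will be presented", in tables that also show severity. The text does not say whether the interval is given by arm.
- Comparison of arms: "Adverse event rates will be compared between the study groups with a Fisher's exact test". By 11.7.2, "The overall significance level for this study is 5% using two-tailed tests".
- Tolerability: "Treatment tolerability will be compared between the study groups", by a method that is not named.

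Serious events are to be discussed one by one, and withdrawals because of AEs are to be counted. The sample size in 11.3 rests on the pain-relief endpoint only.

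SAP section 3 lists safety endpoints. SAP 4.5 fixes the population: "Consequently, the ITT data analysis set will serve as the principal data analysis set for the safety analyses". It repeats the safety analyses on the Full Analysis set. The SAP gives no method for analysing safety.

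**The concern.** An objective to demonstrate safety calls for a statement of how large an excess of events the data can rule out. A Fisher p-value does not supply one. When events are uncommon and the arms are small, a p-value above 0.05 is compatible both with no excess and with a substantial one, and only an interval for the difference tells the reader which excesses remain possible. The planned incidence interval does not do this either, because it describes a rate and not the contrast with sham.

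At stake is what a pivotal clearance trial can say about device-related harm relative to sham. No efficacy conclusion or error rate is affected.

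**Working it through.** **Inputs from the documents.** Two-sided 5% level (protocol 11.7.2). Planned 100 per arm (11.3). About 187 enrolled, taken as 93 per arm (SAP Introduction). About 130 for efficacy, taken as 65 per arm (SAP Introduction).

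The size of the SAP's ITT set, which is principal for safety, is not stated, so 130 is a proxy. The SAP's other figures point the same way: 187 − 50 = 137.

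**Assumptions.** Balanced arms, one yes/no AE outcome per subject, and a sham AE rate that the documents do not give and that is therefore varied.

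**The plan's own sample size.** For 45% against 25%, with pooled variance and 80% power:

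n = [1.96·√(2 × 0.35 × 0.65) + 0.8416·√(0.45 × 0.55 + 0.25 × 0.75)]² / 0.20² = (1.322 + 0.555)² / 0.04, which rounds up to 89 per arm.

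Power at 90 per arm is 80.8%, and 180/(1 − 0.10) = 200. The stated figure reproduces, and it concerns efficacy only.

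**Power of the planned safety test.** This is the sum over all x and y of Bin(x; n, active rate) × Bin(y; n, sham rate), restricted to tables with Fisher p ≤ 0.05:

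| Sham vs active (assumed) | 65 per arm | 93 per arm | 100 per arm |
|---|---|---|---|
| 5% vs 10% | 10% | 17% | 19% |
| 5% vs 15% | 37% | 55% | 59% |
| 10% vs 20% | 28% | 41% | 44% |
| 10% vs 30% | 78% | 92% | 94% |
| 20% vs 40% | 64% | 81% | 84% |

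A doubling is missed more often than not below a sham rate of about 16% (65 per arm) or 11% (100 per arm). A tripling is missed more often than not only below about 6–7% (65 per arm) or 4% (100 per arm). By the pooled formula, 80% power would need 435 per arm for 5% vs 10% and 199 per arm for 10% vs 20%.

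**What an interval would add.** Newcombe 95% limits for d = active − sham, with Wilson limits (l, u) for each arm, are d − √[(p1 − l1)² + (u2 − p2)²] and d + √[(u1 − p1)² + (p2 − l2)²]. For hypothetical counts:

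| Active vs sham | Fisher p | Difference (95% CI), points |
|---|---|---|
| 3/65 vs 3/65 | 1.0 | 0.0 (−8.6 to +8.6) |
| 8/65 vs 3/65 | 0.21 | +7.7 (−2.3 to +18.3) |
| 10/100 vs 5/100 | 0.28 | +5.0 (−2.6 to +13.0) |

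None of these p-values is near 0.05, yet the data would be compatible with an excess of roughly 9, 18 and 13 points respectively.

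**The case against.** The strongest reply is that the primary safety analysis is already estimation: an incidence with a 95% confidence interval, to which Fisher's test is a supplement. The objective in 4.1.3 does not mention sham, and sizing a trial for efficacy while describing safety is ordinary practice. This stands in part. If the interval is given by arm, the upper limit for the active arm is already available; with 0 events in 65 subjects it would be 1 − 0.025^(1/65) = 5.5%. It still says nothing about the excess over sham, which is what the planned comparison of arms addresses.

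A reader might infer that Fisher's test here usually misses a doubling or a tripling. The documents do not support that. They give no AE rate, and protocol 10.1 anticipates local effects such as skin redness, tingling and numbness, so a low sham rate cannot be presumed. At 100 per arm the test detects 5% vs 15% more often than not.

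A reader might also infer that the sponsor plans to take p > 0.05 as proof of safety. No passage says so, and the success rule in 11.7.5 concerns efficacy only. Nor is Fisher's test the only safety comparison of the arms, since tolerability is compared too.

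Finally, both documents are abridged, and a fuller SAP may contain the missing interval. That limits the point to the available text. The protocol's safety paragraph does, however, set out its methods and omits this one.

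**Conclusion.** The point holds in limited form. The objective to demonstrate safety has no criterion, and no estimate or interval is planned for the active-minus-sham excess. The one AE comparison with a stated method is weak for uncommon events: at an assumed 5% sham rate it detects a doubling in 10% to 19% of trials and a tripling in 37% to 59%, over 65 to 100 per arm. For common events the test is adequate against large excesses.

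These figures rest on the assumed sham rate, balanced arms and the efficacy count as a proxy for the safety population. The 93-per-arm column may flatter the Full Analysis set: it assumes one active rate throughout, whereas SAP 4.5 suspects that early treatments were not therapeutic and could lower the event count.

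**What to change.** In the safety part of protocol 11.7.5, and in the SAP for both the ITT and Full Analysis sets:

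1. Report the active-minus-sham difference in the proportion of subjects with any AE and with a device-related AE, each with a two-sided 95% confidence interval (Newcombe or Miettinen–Nurminen).
2. Give the planned incidence interval separately by arm.
3. State that safety is interpreted from the upper limits and that p > 0.05 is not evidence of no excess. Say in advance that the interval governs, because it can disagree with Fisher's test: 10/65 vs 3/65 gives p = 0.076 but an interval of +0.2 to +21.9 points.
4. Reword 4.1.3 as estimating AE incidence and the excess over sham.

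The new column also needs one event window: 4.2.3 uses 24 hours after treatment initiation, while 11.7.5 counts device-related events throughout the study. These should be reconciled.

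The cost is one extra table column and some wording, with no new data and no alpha. The interval does not make the trial more precise; it shows what has not been excluded. The price is a slightly less favourable safety statement.

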ABRIDGED STATISTICAL ANALYSIS PLAN

NEUROLIEF LTD – COMBINED OCCIPITAL AND
SUPRAORBITAL TRANSCUTANEOUS NERVE
STIMULATION FOR TREATMENT OF MIGRAINE
(SP-302-RIME)

31 Aug 2020

AUTHOR:

[name]
BIOSTATISTICIAN

CONTENTS	PAGE
LIST OF ABBREVIATIONS	4
1 Introduction	5
2 Efficacy Endpoints	6
2.1 Primary Efficacy Endpoints.....	6
2.2 Secondary Efficacy Endpoints.....	6
2.3 Additional efficacy endpoints.....	7
3 Safety Endpoints.....	9
4 Analysis Sets	9
4.1 Full Analysis (FA) set.....	9
4.2 Intent-to-Treat (ITT) analysis set.....	9
4.3 Modified Intent-to-Treat (mITT) analysis set.....	9
4.4 Per-protocol (PP) analysis set.....	9
4.5 Statistical Analysis of Analysis Sets.....	10

LIST OF ABBREVIATIONS

Abbreviation or special term	Explanation
AE	Adverse Event
CI	Confidence Interval
FA	Full Analysis
ITT	Intent to Treat
mITT	Modified Intent to Treat
PP	Per Protocol
SAE	Serious Adverse Event
SAP	Statistical Analysis Plan

INTRODUCTION

This Statistical Analysis Plan (SAP) is a more detailed companion to the Statistical Methods section of the study protocol SP-302-RIME (Rev. 2 / June 11, 2019) and provides a comprehensive description of the analysis sets, efficacy endpoints, methods and data analyses to be used. When differences exist in descriptions or explanations provided in the protocol and this SAP, the SAP prevails .

This SAP was finalized before any analysis was performed on the study's clinical data (e.g. interim or final analysis).

Overall, the company has enrolled approximately 187 subjects.

During the initial phase of the study and after a thorough technical investigation a device issue was identified which may have caused ineffective device treatments. To overcome this technical issue, the sponsor performed corrective and preventive actions. Upon resolution, it was decided to exclude from the study data analysis all study treatments performed up to May 31, 2019; these data will still be analyzed separately for safety. As a result of the exclusion of these treatments approximately 50 randomized subjects' efficacy data were lost. To ensure sufficient efficacy evidence, the sponsor communicated the above issue to all ethical committees and received their approval to randomize up to 50 additional subjects to reach the original planned study sample size.

On 02 July 2020 study enrollment was stopped, unfortunately, due to COVID-19; formal notice was sent out to the sites and ethical committees. Even though the company implemented all measures possible to ensure continued screening and randomization, subject retention and minimize loss to follow-up, but found that the completion of the originally planned randomized sample size was impossible .

Therefore, approximately 130 subjects for efficacy analysis were enrolled with 109 that have data for the primary endpoint, but that data remains blinded and has not yet been analyzed.

The approved study analysis plan utilizes a "sample size adaptive design" which calls for a single interim analysis for purposes of sample size adjustment, which was designed to occur when approximately 144 subjects had reached the primary endpoint. Due to the impact of the COVID-19 situation, the company would like to

modify the statistical plan while it remains blinded. The study has been stopped but the interim analysis has not been performed so that only one analysis - the final analysis - will be completed after data lock.

Based on the "Statistical Considerations for Clinical Trials During the COVID-19 Public Health Emergency" June 2020 FDA Guidance, and the fact that the Sponsor remains blinded to the treatment assignment and since no interim analysis was performed, no penalty to the alpha level is required. We shall address further analysis strategies in this revised SAP.

2 **EFFICACY ENDPOINTS**

2.1 **Primary Efficacy Endpoints**

The primary endpoint is the proportion (%) of patients reporting reduction in their pain level 2 hours post-treatment without rescue medications, from severe or moderate to mild or no pain, or from mild to no pain, in their first treated eligible migraine attack (excluding the "self-practice" treatment).

An eligible treatment is defined as a treatment meeting these basic criteria:

- no analgesics or other pain relief drugs or cannabis within 4 hours period before the treatment initiation; and
- no more than 30 minutes passed from the start of the migraine episode; and
- more than 48 pain free hours have passed since subject's previous Migraine episode; and
- subject did not wake up with a Migraine headache; and
- treatment with total stimulation time of at least 30 minutes of a "pass" session on the device log timeline, where pass is defined as a minimal stimulation of 2mA delivered).

2.2 **Secondary Efficacy Endpoints**

Secondary efficacy endpoints include:

1. Proportion of subjects reporting improvement in their most bothersome migraine-associated symptom (MBS) other than a headache, 2 hours post-treatment initiation (if rescue therapy was not used), in their first eligible

treated migraine attack. MBS may be nausea, photophobia, phonophobia as defined by each subject prior to beginning of the treatment.

2. Proportion of subjects reporting reduction of migraine headache pain 1-hour post treatment initiation (if rescue therapy was not used), from severe or moderate to mild or no pain, or from mild to no pain, in their first eligible treated migraine attack.
3. Proportion of subjects who are pain free at 2 hours post treatment initiation (if rescue therapy was not used), in their first eligible treated migraine attack.

2.3

Additional efficacy endpoints

1. Proportion of subjects reporting freedom from their MBS other than a headache, 2 hours post-treatment initiation (if rescue therapy was not used), in their first eligible treated migraine attack.
2. Proportion of subjects who are pain free at 1-hour post treatment initiation (if rescue therapy was not used), in their first eligible treated migraine attack.
3. Proportion of subjects rating the subjects positive (score of 4 or 5) Global Impression of Effect of study device at the end of the study, defined as satisfied or very satisfied using a simple Likert-type scale whereas 1 = Very dissatisfied, 2 = dissatisfied, 3 = unsure, 4 = satisfied, 5 = Very satisfied.
4. Proportion of subjects reporting 2-24h headache relief, defined as headache relief at 2 hours without rescue medications, then no moderate to severe headache in the next 22 hours, and no use of rescue medication or additional stimulation.

Additional efficacy analyses that will be performed

1. Proportion of subjects reporting improvement in their MBS other than a headache AND reduction in their pain level, 1 and 2 hours post-treatment initiation (if rescue therapy was not used), in their first eligible treated migraine attack.
2. Proportion of subjects reporting freedom from their MBS other than a headache AND pain free, 1 and 2 hours post-treatment initiation (if rescue therapy was not used), in their first eligible treated migraine attack.
3. Rescue medicine usage.
4. Proportion of subjects who had pain relief in at least 50% of their eligible treated attacks at each timepoint.

5. Proportion of subjects who were free of pain in at least 50% of their eligible treated attacks at each timepoint.
6. Proportion (%) of attacks for which patients reporting reduction in their pain level without rescue medications from severe or moderate to mild or no pain, or from mild to no pain, from all treated eligible migraine attack at each timepoint (excluding the "self-practice" treatment).
7. Proportion of attacks for which subjects reporting improvement in their MBS other than a headache (if rescue therapy was not used), from all eligible treated migraine attack at each timepoint. MBS may be nausea, photophobia, phonophobia as defined by each subject prior to beginning of the treatment.
8. Proportion of attacks for which subjects reporting pain free (if rescue therapy was not used), from all eligible treated migraine attack at each timepoint.
9. Proportion of attacks for which subjects reporting freedom of MBS other than a headache (if rescue therapy was not used), from all eligible treated migraine attack at each timepoint. MBS may be nausea, photophobia, phonophobia as defined by each subject prior to beginning of the treatment.
10. Proportion (%) of patients with pain level moderate/severe at baseline reporting reduction in their pain level 1, 2 and 24 hours post-treatment without rescue medications, to mild or no pain, in their first treated eligible migraine attack (excluding the "self-practice" treatment).
11. Proportion (%) of patients with pain level moderate/severe at baseline reporting pain freedom at 1, 2 and 24 hours post-treatment without rescue medications, in their first treated eligible migraine attack (excluding the "self-practice" treatment).

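### The only stated power (80% with 180 evaluable subjects) no longer describes the closed trial: chi-square power is about 59-60% at 109 and 67-68% even if all 130 were evaluable, and the supplied SAP does not say so

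*SAP*

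**What the plan says.** Protocol 11.3 (repeated in the Synopsis) assumes 45% responders on active and 25% on sham. It asks for 80% power at a 5% level by chi-squared test and arrives at 180 evaluable subjects, 90 per group, or 200 enrolled after about 10% drop-out. Protocol 11.7.1 makes all tests two-sided. Protocol 11.4 adds one interim look at 144 evaluable subjects, from which the sample size could rise to a maximum of 340.

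The SAP Introduction changes the picture:

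- On recruitment: "Overall, the company has enrolled approximately 187 subjects".
- On the device problem: "As a result of the exclusion of these treatments approximately 50 randomized" subjects' efficacy data were lost.
- On the early stop for COVID-19, it reports that "the completion of the originally planned randomized sample size was impossible".
- On what remains: "approximately 130 subjects for efficacy analysis were enrolled with 109 that have data for the primary endpoint, but that data remains blinded".
- On the interim look: "the interim analysis has not been performed so that only one analysis", the final one, is left.
- On error rates: "since no interim analysis was performed, no penalty to the alpha level is required".

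The Introduction also says: "We shall address further analysis strategies in this revised SAP". The supplied text contains no power, detectable difference or revised sample size for the trial as closed. The document is headed "ABRIDGED STATISTICAL ANALYSIS PLAN". SAP 4.5 makes mITT the principal efficacy set, and SAP 4.3 limits it to subjects who treated at least one eligible attack.

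**The concern.** The SAP takes precedence over the protocol where the two differ. On power it is silent, so 80% at 180 is the only figure on record before unblinding. It belongs to a sample the trial did not reach and to a design with a sample-size increase that can no longer happen. The Introduction covers one consequence of dropping the interim (no alpha adjustment) and leaves out the other (lower power).

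What is at stake is how a non-significant result would be read. Someone relying on 80% would take such a result as fairly strong evidence against a 20-point effect, when the closed trial would miss that effect about two times in five at 109 subjects. A power statement made while the data are blinded is credible. The same statement made after a null result looks like an excuse.

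**Working it through.** **Inputs.** Response rates 0.45 and 0.25, 5% level, 80% power and chi-squared test (Protocol 11.3); two-sided (11.7.1); 1:1 allocation (11.5); 109 and about 130 subjects, and about 187 less about 50 (SAP Introduction). The arm split is not given, so near-equal arms are assumed.

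**Formula.** With p̄ the pooled rate,

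z = [0.20 − 1.96·√(p̄(1−p̄)(1/n₁+1/n₂))] / √(0.45·0.55/n₁ + 0.25·0.75/n₂), and power = Φ(z).

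**1. The plan's own figure.** n per arm = [1.96·√(2·0.35·0.65) + 0.8416·√(0.2475+0.1875)]² / 0.20² = (1.3221 + 0.5551)² / 0.04 = 88.1. The protocol's 90 is sound. At 90/90, z = (0.20 − 0.1394)/0.0695 = 0.872, power 80.8%. And 180/0.9 = 200.

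**2. The 109 with primary data (55/54).** p̄ = 38.25/109 = 0.3509; z = (0.20 − 0.1792)/0.0893 = 0.233; power 59.2%. Reversing the split (54/55) gives 59.3%.

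**3. If all 130 were evaluable (65/65).** z = (0.20 − 0.1640)/0.0818 = 0.440; power 67.0%.

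**4. If all 187 − 50 = 137 were evaluable (69/68).** Power 69.3%.

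**5. Exact check.** Enumerating both binomial distributions gives the power of the chi-square test and of Fisher's test, which Protocol 11.7.5 also plans.

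| Evaluable | Chi-square, formula | Chi-square, exact | Fisher, exact |
|---|---|---|---|
| 109 | 59.2-59.3% | 59.7% | 54.9-56.8% |
| 130 | 67.0% | 68.3% | 61.3% |
| 137 | 69.3% | 69.8% | not run |
| 180 | 80.8% | 81.3% | 76.8% |

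The two Fisher values at 109 depend on which arm has the extra subject. An unpooled normal approximation gives 61.0%, 68.6% and 82.0% at 109, 130 and 180, so the choice of formula moves the answer by one or two points.

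**6. Sensitivity to the split and the count (formula).** At 109, splits of 45/64, 50/59, 59/50 and 64/45 give 58.8%, 59.3%, 58.6% and 57.2%. At 130, splits from 55/75 to 75/55 give 65.4% to 67.1%. Totals of 115, 120 and 125 give 61.6%, 63.5% and 65.2%.

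**7. Detectable difference and precision.** With sham at 25%, power reaches 80% at a difference of 25.8 points (109), 23.5 points (130) and 19.8 points (180). The expected 95% half-width for the difference, 1.96 times the denominator of z, is 1.96·0.0893 = 17.5 points (109), 1.96·0.0818 = 16.0 (130) and 1.96·0.0695 = 13.6 (180).

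**The case against.** The strongest reply is that the plan says nothing false. Protocol 11.3 ties 80% to 180 evaluable subjects, the SAP openly reports the shortfall, and nothing claims that 80% still holds. That is true, and it is why this is an omission and not an error of calculation. The count is disclosed, but its consequence is not.

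Second, the SAP is abridged. Its contents list ends at the analysis sets, and a power update could sit in a section that was not supplied. This stands as a limit: the arithmetic is certain, the absence from the full SAP is not. The fix allows for it.

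Third, enrolment is over and neither the test nor the decision rule changes, so the benefit is confined to the record and to the reading of a null result. Also true. But the data were blinded and unanalysed at the SAP date, so this is prospective power at the design effect, not power computed from an observed effect.

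Fourth, 109 may not be final, and the missing-data part of Protocol 11.7.5 plans multiple imputation. A subject randomized on 02 July 2020 could treat until day 80, about 20 September, after the SAP date of 31 August. Late data would move the figure from 109 towards 130. Imputation would not be expected to restore the information of 130 observed subjects, so 67-68% is best read as an upper bound. Nor does the supplied text show that the 130 − 109 = 21 subjects without primary data belong to the mITT set.

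**Conclusion.** The concern holds. At 45% versus 25%, two-sided 5% and near-equal arms, chi-square power is about 59-60% with 109 evaluable subjects and 67-68% if all 130 were evaluable, against about 81% at 180. The chance of a non-significant chi-square result is 40-41% or 32-33%, against 19%. By Fisher's test it is 43-45% or 39%, against 23%. No plausible arm split changes the conclusion, and even 137 fully evaluable subjects stay below 70% by both chi-square calculations.

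Three assumptions carry this: the arms are near 1:1; 130 and 137 are what-if counts treated as fully evaluable; and every enrolment count except 109 is approximate in the SAP. Type I error and the validity of a positive result are untouched. It should be fixed, but it does not threaten the analysis.

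**What to change.** Before unblinding, add a paragraph to the SAP Introduction along these lines:

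> The 80% power in Protocol 11.3 applied to 180 evaluable subjects and no longer applies. For 45% versus 25% by chi-square, with near-equal arms, power is about 59-60% with 109 evaluable subjects and about 67-68% if all of the approximately 130 were evaluable. With sham at 25%, 80% power applies to a difference of about 26 points (109) to 23.5 points (130).

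If the full SAP already restates power, check it against these figures instead. As an optional addition, report the risk difference with its 95% confidence interval beside the per-arm exact intervals already planned; this shows directly which effects a null result leaves open. The test, the success rule and enrolment stay as they are.

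The cost is one paragraph. The only drawback is that the stated power becomes less favourable.
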